**Table 18 Chi square test of Improvement of >60 m in AWD at three months between treatment groups**

Improvement of >60 m in the AWD at 3 months	NMES + Local available Exercise therapy N=(XX)	Local available Exercises therapy N=(XX)	Total N=(XX)
	Yes	XX (XX.X%)	
	No	XX (XX.X%)	XX (XX.X%)

Imperial Clinical Trials Unit	STATISTICAL ANALYSIS PLAN	NESIC
-------------------------------	---------------------------	-------

**Table 19 Chi square test of Improvement of >100 m in AWD at three months between treatment groups.**  
Same display as Table 18, but for improvement of >100 m in AWD

**Table 20 Summary of Proportion of Patients that improved AWD by more than 60 m by visit and by treatment**

Visit	Improvement of >60 m in the AWD	NMES + Local available	Local available	Total
		Exercise therapy N=(XX)	Exercises therapy N=(XX)	
Baseline	Yes	XX (XX.X%)	XX (XX.X%)	XX (XX.X%)
	No	XX (XX.X%)	XX (XX.X%)	XX (XX.X%)
3 months	Yes	XX (XX.X%)	XX (XX.X%)	XX (XX.X%)
	No	XX (XX.X%)	XX (XX.X%)	XX (XX.X%)
6 months	Yes	XX (XX.X%)	XX (XX.X%)	XX (XX.X%)
	No	XX (XX.X%)	XX (XX.X%)	XX (XX.X%)
12 months	Yes	XX (XX.X%)	XX (XX.X%)	XX (XX.X%)
	No	XX (XX.X%)	XX (XX.X%)	XX (XX.X%)

**Table 21 Summary of Proportion of Patients that improved AWD by more than 100 m by visit and by treatment.** Same display as Table 20, but for improvement of AWD by more than 100 m

**Table 22 Output of Multilevel Tobit model to assess the effects of baseline characteristics for AWD at 3,6, and 12 months**

Fixed Part	Coefficient	SE	z	P> z	95% Confidence interval
AWD(Baseline)	XX.XX	XX.XX	X.XX	X.XXX	X.XX
Treatment	XX.XX	XX.XX	X.XX	X.XXX	X.XX
Time	XX.XX	XX.XX	X.XX	X.XXX	X.XX
Treatment *Time	XX.XX	XX.XX	X.XX	X.XXX	X.XX
Centre	XX.XX	XX.XX	X.XX	X.XXX	X.XX
Group	XX.XX	XX.XX	X.XX	X.XXX	X.XX
Age	XX.XX	XX.XX	X.XX	X.XXX	X.XX
Gender	XX.XX	XX.XX	X.XX	X.XXX	X.XX
BMI	XX.XX	XX.XX	X.XX	X.XXX	X.XX
Smoking status	XX.XX	XX.XX	X.XX	X.XXX	X.XX
_cons	XX.XX	XX.XX	X.XX	X.XXX	X.XX

Random part	Estimate	SE	95% Confidence interval
Between variance	XX.XX	XX.XX	X.XX
Within variance	XX.XX	XX.XX	X.XX

Number of obs = XX, Uncensored = XX, Left-censored= XX, Right-censored = XX

Multilevel Tobit model: Absolute Walking distance (3,6 and 12 months) = intercept + AWD(Baseline) + Treatment + Time + Treatment \*Time + Centre + Group + Age +Gender +BMI +Smoking Status + residual error. Treatment=NMES + local available exercise therapy vs. local available exercise therapy only (1,0), time= variable indicator, one for each follow up period (3 months, 6 months, 12 months) or treat it as time variable, Treatment\*time: Interaction term between treatment and time, Centre=centre identifier, Group= Set or non-SET group (1,0) and Baseline characteristics= Age, gender, BMI, Smoking status.

### 8.9.6 Secondary End Points Analysis

The secondary end points will be analysed for the ITT population and PP population.

Imperial Clinical Trials Unit	STATISTICAL ANALYSIS PLAN	NESIC
-------------------------------	---------------------------	-------

#### 8.9.6.1 Initial Claudication Distance (ICD)

**Table 23 Summary of Initial Claudication Distance (ICD) by visit point and Treatment**

Visit	Treatment	N	Mean	SD	Median	Min	Max
Baseline							
	Treatment  : NMES + EA and NMES+EA+SET	XX	XX.XX	XX.XX	XX	XX	XX
	Control  : EA and EA+SET	XX	XX.XX	XX.XX	XX	XX	XX
3 mths							
	Treatment  : NMES + EA and NMES+EA+SET	XX	XX.XX	XX.XX	XX	XX	XX
	Control  : EA and EA+SET	XX	XX.XX	XX.XX	XX	XX	XX
6 months							
	Treatment  : NMES + EA and NMES+EA+SET	XX	XX.XX	XX.XX	XX	XX	XX
	Control  : EA and EA+SET	XX	XX.XX	XX.XX	XX	XX	XX
12 months							
	Treatment  : NMES + EA and NMES+EA+SET	XX	XX.XX	XX.XX	XX	XX	XX
	Control  : EA and EA+SET	XX	XX.XX	XX.XX	XX	XX	XX

Treatment: NMES + Local Available Exercise Therapy (NMES+EA and NMES+EA+SET)

Control: Local Available Exercise Therapy (EA and EA+SET)

**Table 24 Output of Multilevel Tobit model for Initial Claudication Distance (ICD)**

Fixed Part	Coefficient	SE	z	P> z	95% Confidence interval
ICD(Baseline)	XX.XX	XX.XX	X.XX	X.XXX	X.XX X.XX
Treatment	XX.XX	XX.XX	X.XX	X.XXX	X.XX X.XX
Time	XX.XX	XX.XX	X.XX	X.XXX	X.XX X.XX
Treatment *Time	XX.XX	XX.XX	X.XX	X.XXX	X.XX X.XX
Centre	XX.XX	XX.XX	X.XX	X.XXX	X.XX X.XX
Group	XX.XX	XX.XX	X.XX	X.XXX	X.XX X.XX
Age	XX.XX	XX.XX	X.XX	X.XXX	X.XX X.XX
Gender	XX.XX	XX.XX	X.XX	X.XXX	X.XX X.XX
BMI	XX.XX	XX.XX	X.XX	X.XXX	X.XX X.XX
_cons	XX.XX	XX.XX	X.XX	X.XXX	X.XX X.XX

Random part	Estimate	SE	95% Confidence interval
Between variance	XX.XX	XX.XX	X.XX X.XX
Within variance	XX.XX	XX.XX	X.XX X.XX

Number of obs = XX, Uncensored = XX, Left-censored= XX, Right-censored = XX

Mixed-Effect model: Initial Claudication Distance (ICD) at 3,6 and 12 months = intercept + ICD(Baseline) + Treatment + Time + Treatment

\*Time + Centre + Group + Age +Gender +BMI + residual error. Treatment=NMES + local available exercise therapy vs. local available exercise therapy only (1,0), time= variable indicator, one for each follow up period (3 months, 6 months, 12 months) or treat it as time variable. Treatment\*Time: Interaction term between treatment and time, Centre=centre identifier, Group= Set or non-SET group (1,0) and Baseline characteristics= Age, gender, BMI, Smoking status.

**Table 25 Summary of Proportion of Patients that improved ICD by more than 60 m by visit and by treatment**

Visit	Improvement of >60 m in the ICD	NMES + Local available		Local available Exercises therapy N=(XX)	Total N=(XX)
		Exercise therapy N=(XX)	Local available Exercises therapy N=(XX)		
Baseline	Yes	XX (XX.X%)	XX (XX.X%)	XX (XX.X%)	XX (XX.X%)
	No	XX (XX.X%)	XX (XX.X%)	XX (XX.X%)	XX (XX.X%)
3 months	Yes	XX (XX.X%)	XX (XX.X%)	XX (XX.X%)	XX (XX.X%)
	No	XX (XX.X%)	XX (XX.X%)	XX (XX.X%)	XX (XX.X%)
6 months	Yes	XX (XX.X%)	XX (XX.X%)	XX (XX.X%)	XX (XX.X%)
	No	XX (XX.X%)	XX (XX.X%)	XX (XX.X%)	XX (XX.X%)
12 months	Yes	XX (XX.X%)	XX (XX.X%)	XX (XX.X%)	XX (XX.X%)
	No	XX (XX.X%)	XX (XX.X%)	XX (XX.X%)	XX (XX.X%)

**Table 26 Summary of Proportion of Patients that improved ICD by more than 100 m by visit and by treatment.**  
**Same display as Table 25, but for the Proportion of Patients that improved ICD by more than 100 m**

### 8.9.6.2 Quality of Life scores

See Table 13 and 14 for Summary of Quality of life scores by time point and treatment.

**Table 27 Output of ANCOVA model for changes in Intermittent Claudication score (ICQ-score) from baseline to follow up periods (3,6 and 12 months)**

Source	Partial SS	df	MS	F	Prob>F
Model	XX.XX	XX.XX	X.XX	X.XXX	X.XX
Treatment group indicator	XX.XX	XX.XX	X.XX	X.XXX	X.XX
Baseline measurement	XX.XX	XX.XX	X.XX	X.XXX	X.XX
Residual	XX.XX	XX.XX	X.XX		
Total	XX.XX	XX.XX	XX.XX		
Residual	XX.XX	XX.XX	X.XX	X.XXX	X.XX

**Table 28 Output of ANCOVA model for changes in Quality of life (EQ-5D-5L score) between baseline and follow up periods (3,6 and 12 months).** Same display as Table 27, but for the Quality of life (EQ-5D-5L score). ANCOVA model: Quality of life (EQ-5D-5L score) at 3,6 and 12 months = intercept + treatment group indicator + EQ-5D-5L score (Baseline). Treatment=NMES + local available exercise therapy vs. local available exercise therapy only (1,0).

**Table 29 Output of ANCOVA model for changes in Quality of life (SF-36-score) - Physical function score. between baseline and follow up periods (3,6 and 12 months).** Same display as Table 27, but for the Physical function score from the SF-36 questionnaire. ANCOVA model: Physical function score (SF-36-score) at 3,6 and 12 months = intercept + treatment group indicator + Physical function (Baseline). Treatment=NMES + local available exercise therapy vs. local available exercise therapy only (1,0).

**Table 30 Output of ANCOVA model for changes in Quality of life (SF-36-score) – Role Physical score between baseline and follow up periods (3,6 and 12 months).** Same display as Table 27, but for Role Physical score from the SF-36 questionnaire. ANCOVA model: Role Physical score (SF-36-score) at 3,6 and 12 months = intercept + treatment group indicator + Role Physical score (Baseline). Treatment=NMES + local available exercise therapy vs. local available exercise therapy only (1,0).

**Table 31 Output of ANCOVA model for changes in Quality of life (SF-36-score) – Body Pain score between baseline and follow up periods (3,6 and 12 months).** Same display as Table 27, but for the Body Pain score from the SF-36 questionnaire. ANCOVA model: Body Pain score (SF-36-score) at 3,6 and 12 months = intercept

Imperial Clinical Trials Unit	STATISTICAL ANALYSIS PLAN	NESIC
-------------------------------	---------------------------	-------

+ treatment group indicator + Body Pain score (Baseline). Treatment=NMES + local available exercise therapy vs. local available exercise therapy only (1,0).

**Table 32 Output of ANCOVA model for changes in Quality of life (SF-36-score) – General Health score between baseline and follow up periods (3,6 and 12 months).** Same display as Table 27, but for the General Health score from the SF-36 questionnaire. ANCOVA model: General Health score (SF-36-score) at 3,6 and 12 months = intercept + treatment group indicator + General Health score (Baseline). Treatment=NMES + local available exercise therapy vs. local available exercise therapy only (1,0).

**Table 33 Output of ANCOVA model for changes in Quality of life (SF-36-score) – Vitality score between baseline and follow up periods (3,6 and 12 months).** Same display as Table 27, but for the Vitality score from the SF-36 questionnaire. ANCOVA model: Vitality score (SF-36-score) at 3,6 and 12 months = intercept + treatment group indicator + Vitality score (Baseline). Treatment=NMES + local available exercise therapy vs. local available exercise therapy only (1,0).

**Table 34 Output of ANCOVA model for changes in Quality of life (SF-36-score) – Social functioning score between baseline and follow up periods (3,6 and 12 months).** Same display as Table 27, but for the Social functioning score from the SF-36 questionnaire. ANCOVA model: Social functioning score (SF-36-score) at 3,6 and 12 months = intercept + treatment group indicator + Social functioning score (Baseline).

Treatment=NMES + local available exercise therapy vs. local available exercise therapy only (1,0).

**Table 35 Output of ANCOVA model for changes in Quality of life (SF-36-score) – Role-Emotional score between baseline and follow up periods (3,6 and 12 months).** Same display as Table 27, but for the Role Emotional score from the SF-36 questionnaire. ANCOVA model: Role-Emotional score (SF-36-score) at 3,6 and 12 months = intercept + treatment group indicator + Role-Emotional score (Baseline). Treatment=NMES + local available exercise therapy vs. local available exercise therapy only (1,0).

**Table 36 Output of ANCOVA model for changes in Quality of life (SF-36-score) – Mental Health score between baseline and follow up periods (3,6 and 12 months).** Same display as Table 27, but for the Mental Health score from the SF-36 questionnaire. ANCOVA model: Mental Health score (SF-36-score) at 3,6 and 12 months = intercept + treatment group indicator + Mental Health score (Baseline). Treatment=NMES + local available exercise therapy vs. local available exercise therapy only (1,0).

**Table 37 Output of ANCOVA model for changes in Quality of life (SF-36-score) – Physical Component score between baseline and follow up periods (3,6 and 12 months).** Same display as Table 27, but for the Physical Component score from the SF-36 questionnaire. ANCOVA model: Physical Component score (SF-36-score) at 3,6 and 12 months = intercept + treatment group indicator + Physical Component score (Baseline). Treatment=NMES + local available exercise therapy vs. local available exercise therapy only (1,0).

**Table 38 Output of ANCOVA model for changes in Quality of life (SF-36-score) – Mental Component score between baseline and follow up periods (3,6 and 12 months).** Same display as Table 27, but for the Mental Component score from the SF-36 questionnaire. ANCOVA model: Mental Component score (SF-36-score) at 3,6 and 12 months = intercept + treatment group indicator + Mental Component score (Baseline). Treatment=NMES + local available exercise therapy vs. local available exercise therapy only (1,0).

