**SET Centre randomisation:**

- Best medical therapy including exercise advice and supervised exercise (control 1)  
OR
- Best medical therapy including exercise advice, supervised exercise and neuromuscular electrical stimulation (treatment 1)

Authorised SET centres will be permitted to randomise patients who do not wish to attend [SET classes](#) (i.e. nonSET patients). Therefore, the authorised SET sites will act, for the purposes of these participants, as nonSET sites. In doing so they are still following the basic protocol instructions in that they are providing best medical therapy, as agreed between patient and clinicians, which in this case is not to participate in the SET classes.

At these centres, the InForm database will be linked to a SET and nonSET randomisation list. The appropriate randomisation list will be used by sites dependent on whether the patient is attending / not to attending the SET programme.

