**5.4 Other baseline investigations**

Imperial Clinical Trials Unit	NESIC Clinical Study Protocol V6.0 24/03/2020	Form Number CR001A-T
-------------------------------	---	-------------------------

- **Demographic information & vital signs:** age, ethnicity, date of birth, lifestyle, socioeconomic status, weight, height, blood pressure, pulse
- **Treadmill:** The Gardner-Skinner graded treadmill test will be used (15). The treadmill will start at 3.2 km/h at a 0% incline. Every 2 minutes, the gradient of the treadmill will increase by 2%. Patients will indicate the start of their claudication pain, which will be recorded as the Initial Claudication Distance (ICD) and finally stop the test at the point the patient does not want to continue due to lower limb pain; this is the Absolute Walking Distance (AWD). The patient will not be given a final score to prevent bias. If patients are able to walk for longer than 15 minutes on the treadmill, they will be excluded from the trial.
- **Quality of Life questionnaires:** The validated EuroQoL (EQ-5D-5L) questionnaire and Short Form-36 (SF-36) questionnaire will be used to assess the generic QoL and will allow economic assessment based on intervention and score improvement. The validated Intermittent Claudication Questionnaire (ICQ) will be used to assess change in disease-specific QoL. These should be completed prior to informing the participant of the treatment allocation to prevent bias.
- **Haemodynamic assessment**
  - **Duplex ultrasonography:** Using the appropriate arterial ultrasound probe and pre-set volume flow algorithms on a duplex ultrasound machine, flow within the common femoral artery (CFA), preferably of the most affected limb, will be measured, approximately 5cm below the mid-inguinal point at the groin. Measures include volume flow (VF, cc/min) and time-averaged mean velocity (TAMV, cm/s).
    - **In the control group:** only resting values will be undertaken over a 3-minute period.

Imperial Clinical Trials Unit	NESIC Clinical Study Protocol V6.0 24/03/2020	Form Number CR001A-T
-------------------------------	---	-------------------------

- **The intervention group** will have these parameters measured at rest, at 15 and 30 minutes into device use and then at 1 and 5 minutes after device cessation (16).

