## **5. General Considerations**

### **5.1 Study Design**

The NESIC trial is a pragmatic, multicentre two-arm randomised controlled study stratified by centre. There are 11 participating centres in England, distributed according to local therapy provision between SET and exercise advice only. Initially 5 SET centres and 6 exercise only centres recruited to the trial until all the SET sample of patients was recruited, subsequently 3 SET centres (Imperial, Bristol and Hull) also recruited patients for the exercise only group. Subject to any patient specific restrictions, all participants will receive the best medical therapy (BMT), which include exercise advice, and if the patient has cardiovascular risk factors, then they will aim to control this, e.g. smoking cessation, hypertensive medication and controlling diet.

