## 5.9 Randomization

Once eligibility has been confirmed, subjects will be randomised to one of the two arms of the study and assigned a pseudonymised study number unique to each individual enrolled in the trial.

Randomisation will take place via the InForm system (the electronic case report form database for the study), which will be programmed with a randomisation schedule provided by an independent statistician. Randomisation will be blocked with random block sizes and stratified by centre.

SET CENTRE randomisation:

- Control 1: EA + SET
- Treatment 1: EA + SET + NMES

Non-SET CENTRE randomisation:

- Control 2: EA
- Treatment 2: EA + NMES

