**Table 2 Endpoints and related planned Statistical Analysis Summary**

	End Point	Model
Continuous	Absolute walking distance (AWD) measured by treadmill testing at 3 months (censored at 15 mins and the distance reached to this point is 790 metres) **	Tobit Regression for Absolute walking distance (AWD) at three months with AWD at baseline, treatment indicator, centre and group (SET vs non-SET) as covariates.
	Proportion of patients whose absolute walking distance at 3 months improved by 60 metres or more from baseline	Chi-square test at 3 months
	Proportion of patients whose absolute walking distance at 3 months improved by 100 metres or more from baseline	Chi-square test at 3 months
	Absolute walking distance (AWD) measured at 3, 6, and 12 months. This variable is censored at 15 mins and the distance reached to this point is 790 metres.	Multilevel Tobit model, treating patient as a random effect (repeated measurement) to investigate the relationship between AWD and covariates: AWD baseline measurement Treatment Time Time*Treatment interaction, Centre Group (SET vs non-SET) Age Gender BMI Smoking status
	The proportion of patients who improved AWD at each time point by 
 
• 60 metres or more from baseline
 
• 100 metres or more from baseline
 
	Table of proportion of AWD improvements by treatment and by visit.
Continuous	Initial claudication distance (ICD) measured at 3, 6 and 12 months. This variable is censored at 15 mins and the distance reached to this point is 790 metres.	Multilevel Tobit model Linear mixed-effects model, treating patient as a random effect (repeated measurement) to investigate the relationship between ICD and covariates: ICD baseline measurement Treatment Time Time*Treatment interaction Centre Group (SET vs non-SET) Age Gender BMI
	The proportion of patients who improved ICD at each time point by 
 
• 60 metres or more from baseline
 
• 100 metres or more from baseline
 
	Table of proportion of ICD improvements by treatment and by visit.

Imperial Clinical Trials Unit	STATISTICAL ANALYSIS PLAN	NESIC
-------------------------------	---------------------------	-------

	Quality of Life (QoL)	

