	ICQ health score (calculated using the formulas in Appendix 2 measured at 3, 6 and 12 months	Plot of mean ICQ health score change over time by treatment arm (mean and SD). ANCOVA model for ICQ health score on treatment group indicator, controlling for ICD baseline measurement.
	EQ-5D-5L health score measured at 3, 6 and 12 months	Plot of mean EQ-5D-5L health score changes over time by treatment arm (mean and SD). ANCOVA model for EQ-5D-5L health score on treatment group indicator, controlling for EQ-5D-5L baseline measurement.
	SF36-scores (obtained using software Appendix 2) measured at 3, 6 and 12 months	Plot of mean SF36-scores change over time by treatment arm (mean and SD).
	Section scores Physical function score Role-Physical score Body pain score General Health score Vitality score Social functioning score Role-Emotional score Mental Health score	Separate ANCOVA models for SF36 scores on treatment group indicator, controlling for the baseline measurement of the outcome being analysed.
	Summary scores Physical component scores (PCS) Mental component scores (MCS)	
	Haemodynamic AssessmentT	
	Duplex ultrasonography measure at baseline and 3 months • Mean Volume Flow (VF, cc/min) for one leg (either Right or Left) for each patient • Mean Time average Mean Velocity (TAMV, cm/s) one leg (Left or Right) 2 models	Separate Linear regression models for the Duplex ultrasonography measurements (MVF and MTAMV), using as covariates: Specific baseline measurement Treatment Time Time*Treatment interaction Centre Group (SET vs non-SET) Age Gender BMI
	Laser Doppler Flowmetry (LDF) measure at baseline, 3, 6 and 12 months • Mean Blood flux for one leg (Left or Right)	Separate ANCOVA models for the variables of Laser Doppler Flowmetry (LDF) on treatment group indicator, controlling the baseline measurement of the outcome being analysed.
	Ankle Brachial Pressure Index (ABPI) measure at baseline, 3, 6 and 12 months ABPI for the Left Ankle ABPI for the Right Ankle	Separate ANCOVA models for the variables of Ankle Brachial Pressure Index (ABPI) on treatment group indicator, controlling the baseline measurement of the outcome being analysed.

Compliance with interventions		

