### **8.3 Secondary End Points Analysis**

#### **8.3.1 Continuous Secondary End Point Analysis**

The continuous variables of initial claudication distance (ICD), measured at baseline, 3, 6, and 12 months will be analysed using a Multilevel Tobit model fitted to the censored ICD measurements. The Multilevel Tobit models will be performed to investigate the effect of the treatment indicator on the changes over time (3, 6, and 12 months), treating patient as a random effect, while the baseline measurement of the continuous ICD variable, treatment, time, interaction of time\*treatment, centre, group (SET vs non-SET), age, gender and BMI will be treated as covariates. Results of the Multilevel Tobit model will be presented (see Table 24 Section 8.9.6.1).

A summary table of proportion of patients who increased the ICD both by more than 60 and by more than 100 metres by treatment and by visit will be presented (Table 25 and Table 26)

The secondary end points concerned with quality of life scores (QoL) measured at baseline, 3, 6 and 12 months, will be analysed using separate ANCOVA models for each outcome variable. The measurements of quality of life are the Intermittent Claudication Questionnaire (ICQ), EuroQoL 5D 5L (EQ-5D-5L) and the SF-36.

The ANCOVA models of each of the QoL scores will be performed to investigate changes in QoL over time and to assess the difference between the two treatment groups, while controlling for the baseline measurement of the QoL score being analysed. Results of the ANCOVA models will be presented in tables (see Section 8.9.6.2).

All individual scores for ICQ, EuroQoL 5D 5L and the SF-36 will be presented as Plots. Plots of the mean QoL scores will be used to illustrate changes over time by treatment arm (Figure 1-3, Section 8.10).

Duplex ultrasonography (DU) measurements (Mean Volume Flow and Mean Time Average Mean Velocity) from the Haemodynamic assessment will be analysed using separate linear regression models. The linear regression models will be used to compare the Mean Volume Flow (VF) and Mean Time Average Mean Velocity (TAMV)

Imperial Clinical Trials Unit	STATISTICAL ANALYSIS PLAN	NESIC
-------------------------------	---------------------------	-------

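### LDF and duplex values include on-device readings in one arm only, in the baseline covariate as well as the outcome; separately, the 15 secondary ANCOVAs omit centre and SET group.

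*SAP*

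**What the plan says.** **LDF and duplex.** SAP 7.4 defines LDF blood flux as a mean over the readings ahead of, during and following device use in the device arm, and as a resting value in the control arm. The note to Table 43 confirms that the device-arm figure averages three readings. The note to Table 39 does the same for duplex, with five (rest, 15 and 30 minutes into use, 1 and 5 minutes after). Table 44 (LDF) and Tables 40 and 42 (duplex) use these values on both sides of the model.

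Protocol 5.6 takes LDF on the device at 3 months but only at rest, in everyone, at 6 and 12 months. SAP 7.4 instead attaches the on-device readings to all four visits.

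**Secondary ANCOVAs.** SAP Tables 27-38, 44, 46 and 48 contain treatment and one baseline value, as in "Quality of life (EQ-5D-5L score) at 3,6 and 12 months = intercept + treatment group indicator + EQ-5D-5L score (Baseline". On allocation, SAP 5.9 says "Randomisation will be blocked with random block sizes and stratified by centre". For SET centres that also recruit nonSET patients, protocol 5.3 says "At these centres, the InForm database will be linked to a SET and nonSET randomisation list", and SAP 5.1 records that "subsequently 3 SET centres (Imperial, Bristol and Hull) also recruited patients for the exercise only group". The AWD, ICD and duplex regression models all include centre and group.

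**Wording.** The ICQ row of Table 2 reads "ANCOVA model for ICQ health score on treatment group indicator, controlling for ICD baseline measurement", whereas 8.3.1 fits the quality-of-life models "while controlling for the baseline measurement of the QoL score being analysed". Section 8.3.1 also places duplex under both linear regression and ANCOVA.

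**The concern.** A baseline covariate in a randomised comparison should be measured alike in both arms and be untouched by treatment. Here the device-arm baseline includes readings taken under stimulation, which exist only once allocation is known. The adjustment then removes part of a treatment effect that it should not see.

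At 3 months the outcome has the same asymmetry, so an acute on-device response is counted together with any lasting change. At 6 and 12 months, with rest-only outcomes as in the protocol, an inflated covariate pulls the estimate against the device. The trial could therefore report a microcirculatory benefit at 3 months and harm later when there is no lasting effect at all. Mechanism is a stated secondary objective, so this matters although the endpoint is not primary.

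Leaving centre and group out of the ANCOVAs is a smaller matter of precision and of consistency with the randomisation.

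**Working it through.** **Plan's own figure.** The plan gives none for these endpoints. Its sample size, used below, reproduces: for 60 m with SD 120 m and two-sided 5%, the exact t-test power is 0.8999 at 85 per arm and 0.9032 at 86; 172/0.9 = 191.1, so 192.

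**LDF inputs**
- On-device ratio *k* = 10: protocol 1.8, foot flux, healthy subjects, n = 16. *k* = 2 is assumed.
- Assumed: the after-use reading equals rest; the rise multiplies each patient's own flux; rest-to-rest correlation *r* = 0.3 / 0.5 / 0.7; no lasting effect; resting mean set to 1.

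**Device-arm average relative to rest:** *m* = (1 + *k* + 1)/3. For *k* = 2, *m* = 1.33; for *k* = 10, *m* = 4.0. Control is 1.0.

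**Adjusted difference** = (arm difference in outcome) - *b* x (arm difference in baseline), where *b* is the pooled within-arm slope and the baseline difference is *m* - 1.

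- 3 months: outcome and baseline are both scaled by *m* in the device arm, so *b* = *r* and the shift is (*m* - 1)(1 - *r*).
- 6 and 12 months, resting outcome: *b* = *r*(1 + *m*)/(1 + *m*^2) and the shift is -*b*(*m* - 1). For *m* = 4, *b* = *r* x 5/17 = 0.09 / 0.15 / 0.21. For *m* = 1.33, *b* = 0.84*r* = 0.25 / 0.42 / 0.59.

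| Rise | Visit | Formula, *r* = 0.3 / 0.5 / 0.7 | Simulation |
|---|---|---|---|
| 2-fold | 3 months | +0.23 / +0.17 / +0.10 | +0.24 / +0.17 / +0.10 |
| 2-fold | 6, 12 months | -0.08 / -0.14 / -0.20 | -0.08 / -0.13 / -0.19 |
| 10-fold | 3 months | +2.1 / +1.5 / +0.9 | +2.1 / +1.5 / +0.9 |
| 10-fold | 6, 12 months | -0.26 / -0.44 / -0.62 | -0.25 / -0.43 / -0.61 |

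Units are multiples of resting flux. The simulation used 86 per arm and an assumed between-patient CV of 0.4. A separate run at 6 and 12 months, with ratios 2 to 10 and *r* of 0.3 and 0.6, rejected a true null in 26% to 100% of trials. With the resting reading as baseline in both arms, the mismatch is zero by construction.

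If the on-device readings were also used at 6 and 12 months, as SAP 7.4 says, the 3-month row would apply there and the sign would reverse.

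**Duplex, illustration only.** Protocol 1.6 cites an 84% rise in arterial flow with another NMES device in 10 healthy people. If the two on-device readings are 1.84 times rest and the other three equal rest, *m* = (3 + 2 x 1.84)/5 = 1.34. That is close to the 2-fold LDF case.

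**Count of ANCOVAs.** ICQ 1 + EQ-5D-5L 1 + SF-36 10 + LDF 1 + ABPI 2 = 15.

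**Cost of omitting the strata.** Let *f* be the share of residual variance due to strata (assumed). Ignoring the cost of extra terms, the SE ratio is 1/sqrt(1 - *f*) = 1.026 at 5% and 1.054 at 10%. SAP 5.1 implies 5 + 6 + 3 = 14 centre-by-list strata. A simulation with 14 strata of assumed unequal size, 192 randomised and 172 analysed, counts that cost. The ratio, unadjusted to adjusted, is 0.995 at *f* = 0, 1.017 at 5% and 1.041 at 10%.

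**The case against.** The best defence is that the on-device contrast was intended: protocol 1.6 plans LDF at rest in controls and through device use in the intervention group. That stands to the extent that an acute on-device comparison at 3 months is a legitimate question, and calling the whole difference false presumes that a lasting effect is the target. It does not rescue the model. The baseline covariate is still contaminated in one arm, and an average of resting and stimulated readings estimates neither the acute nor the lasting effect.

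Several stronger readings are tempting and are not supported.

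- **Larger late shifts.** A reader might apply slopes of 0.3 / 0.5 / 0.7 to a baseline gap of 3 and infer -0.9 / -1.5 / -2.1 at 6 and 12 months for a 10-fold rise. That needs the device to add the same constant in every patient. The protocol's figure is a ratio, which also widens the baseline spread and flattens the slope to 0.09-0.21.
- **Bias in all 15 models.** Quality of life and ABPI are measured alike in both arms, and protocol 5.4 says of the baseline questionnaires: "These should be completed prior to informing the participant of the treatment allocation to prevent bias". Omitting strata there loses a little precision and makes the test slightly conservative.
- **Visits stacked as independent.** Each formula carries three visits, and Table 27 has one treatment row. But where the SAP pools visits it says so, as for ICD: "treating patient as a random effect (repeated measurement) to investigate the relationship between ICD and covariates". Separate fits per visit are the more natural reading, so only a clarification is needed.
- **Wrong ICQ covariate.** Section 8.3.1 makes the intended covariate clear; the Table 2 entry is a slip.

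The 14 strata are also uncertain. Protocol 4.1 makes St George's a dual centre and Bournemouth non-SET, while SAP Table A1 lists Bournemouth as a SET centre and omits St George's.

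**Conclusion.** The LDF and duplex definitions are wrong as written for a between-arm comparison of lasting effect. The direction for LDF does not depend on the assumed values so long as flux rises during use and resting flux is positively but imperfectly correlated across visits: towards the device at 3 months, and against it at 6 and 12 months if those outcomes are taken at rest. The size does depend on them. With no lasting effect and after-use flux back at rest, a 2-fold rise gives about +0.24 to +0.10 and then -0.08 to -0.19 times resting flux; a 10-fold rise gives about +2.1 to +0.9 and then -0.25 to -0.61. The 10-fold figure comes from healthy subjects and may not carry over to patients with claudication. The disagreement between SAP 7.4 and protocol 5.6 over the 6 and 12-month readings must be reconciled, since the later sign depends on it.

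The missing centre and group terms are a cheap improvement, not an error that biases results: 2% to 4% in SE if strata explain 5% to 10% of residual variance, against a cost of about 0.5% if they explain nothing. The remaining items are wording. All the affected endpoints are secondary or mechanistic, so this should be changed but does not threaten the main result.

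**What to change.** 1. In SAP 7.4 and Tables 39-44, use the resting reading in both arms as baseline covariate and as between-arm outcome, for LDF and for duplex. Report on-device readings as a description within the device arm. If an on-device contrast at 3 months is also wanted, label it as such and still adjust for the resting baseline.
2. Reconcile SAP 7.4 with protocol 5.6 on which LDF readings are taken at 6 and 12 months.
3. Add centre and SET group to all 15 ANCOVAs, as in the AWD, ICD and duplex regression models.
4. State that each ANCOVA is fitted separately by visit, or specify a mixed model with a patient term.
5. In the ICQ row of Table 2, replace the ICD baseline with the ICQ baseline. Keep one duplex model in 8.3.1.

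The cost is SAP wording and table shells. No new data are needed: protocol 5.4 already takes resting duplex and LDF readings in both arms.
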